#### 4.2.4 Medical History

Relevant medical history (past and current) and relevant surgical history will be coded using the latest version of MedDRA.

All medical history will be summarised (number and percentage of patients) for the FAS by system organ class (SOC) and preferred term (PT).

All relevant surgical history will be summarised similarly.

#### 4.2.5 Concomitant Medication / Treatment

Concomitant medications are those with a stop date on or after the first dose date of study treatment or those that are marked as ongoing (and could have started prior to or during treatment).

Concomitant medication / treatment will be summarised using frequency tables by anatomical therapeutic chemical classification (ATC) code.

#### 4.2.6 Exposure and Compliance to AZD9291

Exposure (total and actual) to AZD9291 will be summarised in months for the FAS and for discontinued patients as a continuous variable and by class (<3; [3-6[; [6-12[; [12-18[; >=18 months).

##### **Total Exposure Plot**

A plot giving the decreasing percentage of patients still on treatment against time (months) will be presented.

##### **Compliance**

Treatment compliance is calculated as the proportion in percentage of the scheduled expected number of doses, i.e. (Actual exposure/Total exposure)\*100.

Compliance will be summarised as a continuous variable for the FAS.

#### 4.2.7 Efficacy

##### **Overall Survival (OS)**

Overall survival will be summarised using Kaplan-Meier (KM) estimates of the median time to death or censoring and quartiles together with their 95% confidence intervals. Kaplan-Meier estimates of the OS rate at appropriate time points (see Event rate at fixed time point) will be presented as well.

A plot of the KM OS curve will be produced, including tickmarks to identify censored observations and numbers of patients at risk.

The number of patients prematurely censored will be summarised. A patient would be defined as prematurely censored if moving to commercial supply or if their survival status was not defined at the date of study discontinuation and if his/her last available information in the CRF is more than 6 weeks prior to the study discontinuation.

In addition, duration of follow-up will be summarised:

- In censored patients who are alive at the last assessment before study discontinuation only: Time from date of first dose of AZD9291 in this study to date of censoring (date last known to be alive).
- In prematurely censored patients: Time from date of first dose of AZD9291 in this study to date of censoring.

- In all patients: Time from date of first dose of AZD9291 in this study to the date of death (i.e. overall survival) or to the date of censoring for censored patients.

### ***Progression Free Survival (PFS)***

Progression Free Survival will be summarised similarly to OS using Kaplan-Meier (KM) estimates of the median time to progression or death (by any cause in the absence of progression) and quartiles together with their 95% confidence intervals. KM estimates of the PFS rate at appropriate time points (see Event rates at fixed time points) will be presented as well.

Progression free survival events will be divided into 3 categories: Progression, Death due to disease progression, and Death due to reasons other than disease progression. Patients who have a progression event recorded in the tumor evaluation CRF will be summarised under 'Progression'. Patients with no progression event recorded in the tumor evaluation CRF but who have died with the cause of death assessed as due to disease progression as per list defined in appendix 5 will be summarised under 'Death due to disease progression', and patients who have died due to other causes will be summarised under 'Death due to reasons other than disease progression'.

Patients who have no progression or death record entered into the relevant CRF will be censored as described in section 3.1.2.

A plot of the KM PFS curve will be produced, including tickmarks to identify censored observations and numbers of patients at risks at each specific fixed time points (see Event Rates at Fixed Time Points).

The treatment status on the date of progression/death or censoring of patients will be summarised.

This will include the number (%) of patients who were on treatment at the time of progression, the number (%) of patients who discontinued study treatment prior to progression, the number (%) of patients who had not progressed and were on treatment or discontinued treatment at time of censoring.

Additionally, the number (%) of patients who continue on study treatment after progression will be summarised.

Patients are considered as continuing treatment after progression if stop date is more than 7 days after progression date.

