- (d) Before initiating treatment with AZD9291 the T790M mutation status after progression needs to be known. T790M mutation test may have been done per routine practice earlier than 28 days prior to day 1 as long as this was obtained following the progression on prior TKI therapy (patients may also have received additional lines of treatment).
- (e) For subjects withdrawn from treatment but who had not progressed at the time of AZD9291 discontinuation. Follow up to be performed every 6 weeks ( $\pm 1$  week) relative to the date of enrolment until end of study (including survival follow-up period).
- (f) Pregnancy test to be performed in accordance with local standards
- (g) Survival status to be performed every 6 weeks ( $\pm 1$  week) relative to the date of enrolment until end of study

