## **9.2 Description of outcome variables in relation to objectives and hypotheses**

Analysis will be conducted to evaluate the following as available in the CRF:

- Baseline characteristics: demographics, relevant medical history, disease characteristics, cancer treatment history.
- Exposure to AZD9291
- Response Rate (RR):  
RR is defined as the percentage of patients with a best response of ‘responding’ by investigator assessment as recorded in the CRF.
- Overall Survival (OS):  
Overall survival is defined as the time from the date of first dose of AZD9291 in this study until death due to any cause. Any subject not known to have died at the time of analysis will be censored based on the last recorded date on which the subject was known to be alive.
- Progression Free Survival (PFS)  
PFS is defined as the time from first dose of AZD9291 in this study until the date of disease progression as recorded in CRF or death (by any cause in the absence of progression) regardless of whether the subject withdraws from therapy or receives another anti-cancer therapy prior to progression. Subjects who have not progressed or died at the time of analysis will be censored at the time of the latest date of assessment.
- Time to treatment discontinuation (TTD):  
TTD is defined as the time from the date of first dose of AZD9291 in this study until the date of AZD9291 discontinuation for any reason including disease progression, treatment toxicity, death or other reason as recorded in CRF. Subjects who are still on treatment at the time of analysis will be censored at the date of last dose received.
- Adverse events  
Serious Adverse Events [SAEs], adverse events leading to dose modification, and adverse events of special interest

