##### **3.1.2 Progression Free Survival (PFS)**

Progression Free Survival is defined as the time from the date of first dose of AZD9291 in this study until the date the disease is considered by the investigator to be progressing (as recorded in the tumour evaluation CRF and irrespective of the method of evaluation) or the date of death (by any cause in the absence of progression) regardless of whether the patient withdraws from therapy or receives another anti-cancer therapy prior to progression (i.e. date of disease progression or death – date of first dose of AZD9291 in this study + 1). Patients who have not progressed or died at study discontinuation will be censored at the time of the latest date of disease assessment. Patients with no post baseline disease assessment will be censored at Day 1.

The PFS time will always be derived based on the date of tumour assessment or death and not visit dates.

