### 3.1.3 Time to Treatment Discontinuation or Death (TTD)

As a supportive summary to PFS, time to treatment discontinuation or death will be assessed and is defined as the time from the date of the first dose of AZD9291 in the study until the date of AZD9291 discontinuation (as recorded on the discontinuation of study drug CRF) or death, regardless of the reason for discontinuation (disease progression, treatment toxicity or other reason as recorded in the CRF). This will be calculated as: date of AZD9291 discontinuation or death – date of first dose of AZD9291 + 1. Patients who transitioned to commercial supply will be censored at the date of discontinuation of study treatment (date of their last dose of study treatment).

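### PFS does not use a stop for disease progression that lacks a progressing entry on the tumour evaluation CRF; count these patients and add one sensitivity analysis

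*SAP*

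**What the plan says.** Protocol 9.2 runs PFS from first dose "until the date of disease progression as recorded in CRF or death", without naming a form. SAP 3.1.2 names one: progression is the investigator's judgement "as recorded in the tumour evaluation CRF and irrespective of the method of evaluation". It adds that PFS is derived from tumour assessment or death dates, not visit dates.

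SAP 4.2.7 sorts the remaining patients. "Patients with no progression event recorded in the tumor evaluation CRF but who have died" are events at death, labelled by cause. For the others, "Patients who have no progression or death record entered into the relevant CRF will be censored as described in section 3.1.2". That section reads: "Patients who have not progressed or died at study discontinuation will be censored at the time of the latest date of disease assessment", or at Day 1 if no assessment followed baseline.

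The reason for stopping AZD9291 is collected separately. SAP 3.1.3 counts discontinuation or death as a TTD event, "regardless of the reason for discontinuation (disease progression, treatment toxicity or other reason as recorded in the CRF"). SAP 4.2.1 tabulates the main reason for stopping. Neither record feeds PFS.

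After the stop, the progression follow-up column of Protocol Table 4 is, by footnote (e), "For subjects withdrawn from treatment but who had not progressed at the time of AZD9291 discontinuation". Protocol 4.3.1 likewise asks for continued tumour assessments only when the stop was for another reason.

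**The concern.** A patient can be off drug because the investigator judged the disease to have progressed, yet have no progressing entry on the one form that PFS reads. Once the stop is attributed to progression, no later scheduled assessment would supply the entry. PFS then treats the patient as progression-free until death, or censors at the last assessment because the progression was noted elsewhere. That censoring is informative.

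The estimated median and fixed-time PFS rates would be too high by an unknown amount. TTD, which SAP 3.1.3 calls supportive of PFS, would count the same stop as an event, so part of any gap between the two curves would be a recording artefact. The treatment-status table in SAP 4.2.7 could also show such a patient as not progressed at censoring. No PFS sensitivity analysis is specified; the one defined for efficacy concerns response rate (SAP 3.1.4 and 4.2.7).

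**Working it through.** The plan states no PFS size, event count or precision to reproduce. The check follows the rule through and then illustrates its effect.

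**Tracing the rule.** Let L be the last tumour evaluation (not progressing), S the stop for progression and D death, with L < S < D.

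- Death on record: PFS event at D. The event is late by D − S.
- No death on record: censored at L. The patient's own time is shorter, but a patient at the point of progressing leaves the risk set without an event, so the estimated curve rises.
- No evaluation after baseline and no death on record: censored at Day 1, with the same effect.

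**Inputs from the documents**

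- Median PFS 9.6 months: preliminary background figure, 41 of 138 events (Protocol 1.4.2).
- Median OS 21, 23 or 25 months; study length 58 months; accrual over 40 months (SAP 1.3). Follow-up is then 58 − 40 = 18 to 58 months.
- Tumour evaluation about every 12 weeks (SAP 3.1): 84 / 30.4375 = 2.76 months.

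**Assumptions not in the documents**

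- PFS and post-progression survival are exponential, the latter tuned to the OS median.
- 10% of PFS events are deaths without progression.
- Follow-up is uniform over 18–58 months (the plan has non-uniform accrual).
- A share f of progressions, from 0 to 30%, has no tumour-form entry.

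**Hand check, all affected patients censored.** If censoring fell exactly at progression, the event hazard would fall by the factor 1 − 0.9f, so the median would be 9.6 / (1 − 0.9f):

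- f = 5%: 9.6 / 0.955 = 10.05
- f = 10%: 9.6 / 0.91 = 10.55
- f = 20%: 9.6 / 0.82 = 11.71
- f = 30%: 9.6 / 0.73 = 13.15

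Censoring at the last evaluation removes patients somewhat sooner, so the simulated values should lie slightly below these.

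**Simulation, 200,000 patients, OS median 23 months**

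| f | Median, SAP rule | Shift | 12-month PFS, SAP rule | Median if all affected are censored |
|---|---|---|---|---|
| 0% | 9.60 | 0 | 42.1% | 9.60 |
| 5% | 10.01 | +0.41 | 43.6% | 10.00 |
| 10% | 10.47 | +0.87 | 45.2% | 10.46 |
| 20% | 11.50 | +1.90 | 48.4% | 11.56 |
| 30% | 12.51 | +2.91 | 51.5% | 12.81 |

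With OS medians of 21 and 25 months, the shifts under the SAP rule, each against the true median in the same simulated set (9.55 and 9.61), are:

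- f = 5%: 9.97 − 9.55 = +0.42 and 10.04 − 9.61 = +0.43
- f = 10%: 10.38 − 9.55 = +0.83 and 10.54 − 9.61 = +0.93
- f = 20%: 11.31 − 9.55 = +1.76 and 11.56 − 9.61 = +1.95

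The shift depends mainly on f, and little on which branch applies. Counting the stop as an event recovers the true curve by construction, because the simulation sets the stop date equal to the progression date; in practice it would do so only approximately.

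**The case against.** The strongest reply is that the plan already asks for the missing entry. The tumour evaluation CRF is not a scan form: it takes the investigator's opinion, with clinical examination among the listed methods (SAP 3.1). Protocol Table 4 schedules investigator-reported efficacy at every treatment visit and at treatment discontinuation. Protocol 4.1 item 5c requires it in the CRF, and Protocol 5 has the physician date progression and record the method. This stands: the problem needs a site to omit a required record. Mismatches may also be queried under the Data Management Plan, which is not among the documents. But nothing in the protocol or SAP requires the stopping reason to be reconciled with the tumour form.

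Four stronger readings are tempting and not supported:

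- *That clinical progression between scans cannot be recorded.* It can, for the reasons just given.
- *That the SAP anticipates these patients because it has a category for death due to progression without a tumour-form entry.* The category equally fits patients who die of lung cancer between assessments or before any.
- *That naming the tumour form is an undeclared change from the protocol.* Protocol 5 describes progression date and method under disease assessment, so SAP 3.1.2 can be read as making "the date of disease progression as recorded in CRF or death" operational. Nothing shows that the discontinuation form holds a progression date.
- *That the stop date should replace the main progression date.* Treatment beyond progression is allowed (Protocol 4.3.1), Protocol 4.3 groups progression with loss of clinical benefit as grounds for stopping, and SAP 3.1.2 deliberately uses assessment dates.

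Consequences are also limited: PFS is secondary, single-arm and descriptive, and TTD counts these stops.

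**Conclusion.** The gap is real but conditional. Where drug is stopped for progression and no progressing entry is made, the SAP dates the PFS event at death or censors informatively, and both push the Kaplan-Meier estimate upward. No analysis shows how many patients this affects.

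The size rests on a share that the documents do not give. It is nil at 0%, about +0.4 months at 5% and about +0.9 at 10%, from a 9.6-month median and under the stated assumptions. The larger shares show only how the shift scales. A reader might infer that reported PFS is overstated by about a month; the documents do not support that, since the true share may be near zero. What they do support is that the bias has one direction and can be counted from data already collected. It is a modest, inexpensive improvement to a secondary endpoint.

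**What to change.** Leave the PFS definition in SAP 3.1.2 as it is. In SAP 4.2.7 add:

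1. The number (%) of FAS patients whose recorded reason for stopping AZD9291 is disease progression and who have no progressing tumour evaluation at any time, split into PFS event at death, censored at the last assessment and censored at Day 1.
2. A pre-specified PFS sensitivity analysis in which these patients, and only these, have an event at the AZD9291 discontinuation date. Patients with a progressing entry keep its date, even if it falls after the stop. Report the median, quartiles and fixed-time rates beside the main analysis.

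A count near zero would show that the main PFS result is not exposed to this problem; otherwise the two estimates show how far it matters.

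The cost is a short SAP addition, a small derivation and one more set of Kaplan-Meier output, with no new data. The stop date only approximates the progression date, which is why this belongs in a sensitivity analysis.

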### ***Time to Treatment Discontinuation or Death (TTD)***

As for OS, Time to Treatment Discontinuation or death will be summarised using Kaplan-Meier (KM) estimates of the median time to treatment discontinuation or death and quartiles together with their 95% confidence intervals. KM estimates of the rate of patients still on treatment at appropriate time points (see Event Rates at Fixed Time Points) will be presented as well.

A plot of the KM estimates of TTD will be produced, including tickmarks to identify censored observations and numbers of patients at risks at each time point.

**Event Rates at Fixed Time Points**

For OS, PFS and TTD, event rates will be presented at specific fixed time points. Initially an interval of 3 months will be chosen extended to 6 months after 18 months: 3, 6, 9, 12, 15, 18, 24, 30, 36 months, but this may be adjusted appropriately according to the distribution of the time-to-event variable and follow-up time.

**Response Rate**

Response rate, as defined in Section 3.1.4, will be summarised together with exact 95% confidence interval using the Clopper-Pearson method, based on a subset of the FAS consisting of patients with at least one documented response assessment. The Best Overall Response (responding, stable disease, progressing, not evaluated) will also be summarised. A sensitivity analysis of response rate will also be performed including patients who died prior to any documented response assessment and classifying them as non-responders.

**Evaluation of Brain/Leptomeningeal Metastases at Progression (regardless of site of progression)**

Brain/leptomeningeal metastases at progression (*regardless of site of progression*) will be summarised separately for patients with presence and absence of brain/leptomeningeal metastases at screening for patients who have a baseline assessment of brain/leptomeningeal metastases:

- For patients without brain/leptomeningeal metastases at screening, the method of assessment, presence of a lesion at progression and sites of lesions (Brain/Leptomeningeal) will be summarised.
- For patients with brain/leptomeningeal metastases at screening, the method of assessment and status at progression will be summarised.

**Subgroup Analyses**

Demographics, OS, PFS, TTD and RR will be analysed in the following subgroups of the FAS:

Subgroup	Demo-graphics	OS	PFS	TTD	RR
• Sex (male ; female)	√	√	√	√	√
• Age at enrolment (<75 ; ≥75 years of age)	√	Summary of cause of death	√	√	√
• Race (White, Black, Asian, and Other).	√		√	√	√
• Ethnicity (Asian, non-Asian).	√	√	√	√	√
• Country of enrolment	√		√	√	√
• WHO Performance Status (<2; =2)	√	√	√	√	√

Subgroup	Demo-graphics	OS	PFS	TTD	RR
• Prior Lines of therapy (one line ; more than one line)	√		√	√	√
• Mutation combinations as defined in section 4.2.3: (T790M only ;Common mutations Uncommon / Compound mutations)	√		√	√	√
• Mutation Status (Any compound mutations with a sample size of at least 50 patients (n≥50))	√		√	√	√
• Sample Type for receptor status assessment (Plasma ; Tissue ; Other)	√	√	√	√	√
• Type of T790M testing (Roche cobas® test on plasma ; Every other test on plasma with at least 50 patients ; Roche cobas® test on tissue ; Every other test on tissue with at least 50 patients)	√		√	√	√
• Brain/leptomeningeal metastases status at baseline (Present ; Absent ; Not Done)	√	√	√	√	√
○ Prior radiotherapy (Y/N) in Brain/leptomeningeal metastases subgroup	√		√		√
• Prior Type of anti-cancer therapy (TKI alone  ; TKI + Other anti-cancer therapy  )	√	√	√	√	√
• Prior Type of TKI (TKI first generation only ; TKI second generation only ; TKI first generation + TKI second generation, TKI first generation and/or second generation + TKI third generation)	√		√	√	√
• Prior chemotherapy (Yes  ; No)	√	√	√	√	√
○ Line of Chemotherapy (First line; Second line; Third line or more)	√		√	√	√

TKI alone does not refer to monotherapy, but only ever having previously received a TKI and no other anti-cancer treatment in the metastatic setting.

 Other anti-cancer therapy includes any anti-cancer treatment other than a TKI, palliative radiotherapies and surgery associated with advanced lung cancer as defined in Appendix 6.

 Subgroup Prior chemotherapy = Yes includes all patients previously treated by chemotherapy other than adjuvant or neo-adjuvant only.

Subgroup	Demo-graphics	OS	PFS	TTD	RR
• Use of TKI in patients with prior first or second line chemotherapy (Yes; No)	√		√	√	√

The subgroup analyses will be based on the values recorded on the CRF.

The subgroup analyses for time-to-event endpoints will be performed only for the subgroups with 20 events or more.

The summary of cause of death by age class will include disease under study, AEs not considered related to AZD9291, AEs considered related to AZD9291, Other. Deaths due to disease under study are defined as deaths due to disease progression as defined in the list in Appendix 5.

A swimmer plot for PFS will be produced for the uncommon/compound mutation subgroup and a listing of PFS for patients with T790M + Exon 20 Insertion only will be presented.

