## 5. STUDY MEASURES

The sources of information for all study variables collected for this study will be patient medical records or charts and patients surveys. All data collected will be entered by the investigator into a CRF. All patients participating in the study will be followed from enrolment until completion of the study, discontinuation of AZD9291 administration (determined by investigator due to adverse events, toxicities or other relevant reasons), discontinuation due to disease progression, or death, whichever occurs earlier.

Study measures will be collected at baseline and during the follow-up period. For each patient, physicians will be required to provide date of enrolment, and thereafter during the follow-up visits, the date and outcome of the more recent disease assessment, and date of progression and death (if applicable). The variables described in the following sections will be collected to address the study objectives.

The study measures that will be assessed among patients participating in this study are listed below:

- **Baseline demographic characteristics:** patient characteristics including age, gender, race (if available or allowed by local regulations) will be collected
- **T790M** positive mutation status results and type of test performed and receptors

- **Relevant Medical history:** comorbidities and relevant medical history (this includes any chronic conditions currently requiring medication)
- **Physical examination:** at baseline and at treatment discontinuation
- **Weight:** at each visit
- **Visual test:** at screening, a slit-lamp examination should be obtained. Ophthalmologic exams to be performed as clinically indicated. A 30-day follow-up assessment will be required if an on treatment assessment was abnormal at the time of discontinuation of study therapy, to confirm reversibility of the abnormality.
- **Disease characteristics:** tumor histology, stage at diagnosis, current stage, presence of leptomeningeal /brain metastases at baseline, WHO performance status at study enrollment and subsequent follow-up visits
- **Cancer treatment history:** first-line therapy type (targeted or non-targeted) and agents received, start and end-dates, subsequent-lines type and start and end-date, radiation therapy (yes/no), surgery (yes/no) received prior to study enrollment must be documented

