Previous anti-cancer treatments will be summarised by category: TKI, Chemotherapy, Immunotherapy, Antiangiogenic therapy, Other anti-cancer treatment.

Lists of possible TKIs, Chemotherapy agents, Immunotherapy agents and Antiangiogenic therapies are provided in Section 9. All other anti-cancer treatments that are not listed in Section 9 are considered in the Other therapies category.

Previous radiotherapies and previous surgeries will also be summarised.

Previous surgeries will be summarised by category: associated with advanced lung cancer: not associated with advanced lung cancer.

List of surgeries associated with advanced lung cancer is provided in Section 9. All other surgeries not listed in Section 9 are considered as not associated with advanced lung cancer.

Additionally, the following derived variables will be summarised:

- Age at study enrolment as a continuous variable
- Age at study enrolment by class ( <50; >=50 - <65; >=65 - <75; >=75 - <80, >=80 and <65; >=65)
- Duration from most recent receptor status assessment for T790M mutation to study enrolment (months)
- Duration from original lung cancer disease diagnosis to study enrolment (months)
- Duration from last TKI exposure to study enrolment (<= 6 months, > 6 months)
- Duration from last dose of prior cancer therapy to study enrolment (months)
- Duration from scan for evaluation of brain/leptomeningeal metastases to study enrolment (months)
- Duration from last dose of prior anti-cancer therapy to most recent receptor status for T790M mutation (months)

Enrolment date corresponds to the date enrolment ID and AZD9291 are allocated to the subject in Interactive Web Response System (IWRS). Enrolment date may be prior to first dose date of AZD9291.

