## 6. Surgeries associated with advanced lung cancer:

Preferred term
Lung lobectomy
Lymphadenectomy
Pulmonary resection
Lung neoplasm surgery
Pneumonectomy
Brain tumour operation
Pleurectomy
Hepatectomy
Adrenalectomy
Bone lesion excision
Vertebroplasty
Brain lobectomy
Internal fixation of spine
Lymphoid tissue operation
Metastases to central nervous system
Pericardial drainage
Pericardial effusion malignant
Pleural adhesion
Pleural decortication
spinal corpectomy
Spinal decompression
Tracheal resection
Tumour excision
Ventriculo-pleural shunt

- **Protocol number:** D5160C00022
- **Document title:** Open Label, Multinational, Multicenter, Real World Treatment Study of Single Agent AZD9291 for Patients with Advanced/Metastatic Epidermal Growth Factor Receptor (EGFR) T790M Mutation-Positive Non-Small Cell Lung Cancer (NSCLC) Who Have Received Prior Therapy with an EGFR Tyrosine Kinase Inhibitor (EGFR-TKI).
- **Version numbers:** SAP Addendum Version 1.0
- **Date of the documents:** 03 Nov 2020
- **NCT number:** NCT02474355

Statistical Analysis Plan 7.0 – Addendum 01  
Study code D5160C00022  
Version 1.0  
Date 03 November 2020

---

**Real World Treatment Study – Statistical Analysis  
Plan (for the final analysis) – Addendum 01**

Drug Substance	AZD9291
Study Code	D5160C00022
Version Number	1.0
Date	03 November 2020

---

---

***Open Label, Multinational, Multicenter, Real World Treatment Study of Single Agent AZD9291 for Patients with Advanced/Metastatic Epidermal Growth Factor Receptor (EGFR) T790M Mutation-Positive Non-Small Cell Lung Cancer (NSCLC) Who Have Received Prior Therapy with an EGFR Tyrosine Kinase Inhibitor (EGFR-TKI)***

---

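### SAP 4.2.7 footnotes 1 and 2 do not define complementary groups, so patients with only adjuvant therapy or an earlier listed resection before their TKI can fall in either 'TKI alone' or 'TKI + Other'

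*SAP*

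**What the plan says.** The subgroup table in SAP 4.2.7 has a row for prior type of anti-cancer therapy with two levels, ticked for demographics, OS, PFS, TTD and RR. Its definitions are in footnotes.

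- Footnote 1 defines 'TKI alone' as "only ever having previously received a TKI and no other anti-cancer treatment in the metastatic setting".
- Footnote 2 defines the other level: "Other anti-cancer therapy includes any anti-cancer treatment other than a TKI, palliative radiotherapies and surgery associated with advanced lung cancer", with the surgery list in Appendix 6.
- Footnote 3 belongs to a separate row, prior chemotherapy. It counts as Yes "all patients previously treated by chemotherapy other than adjuvant or neo-adjuvant only".

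SAP 4.2.3 uses the same split for the receptor-status summary. It repeats the footnote 2 description without footnote 1's limit. It also classifies surgery by list membership: "All other surgeries not listed in Section 9 are considered as not associated with advanced lung cancer". Appendix 6 contains "Lung lobectomy", pulmonary resection, pneumonectomy and lymphadenectomy beside metastasis-directed and palliative terms. It gives no condition on date, stage or intent.

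The protocol synopsis describes the cohorts as based on lines of treatment given for advanced disease. Protocol section 5 collects "stage at diagnosis, current stage". It lists start and end dates for lines of therapy, but lists prior surgery and radiotherapy only as yes/no.

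**The concern.** A two-level split needs one boundary, and here each level has its own. 'TKI alone' looks only at the metastatic setting. 'Other' takes in systemic therapy from any setting, and any surgery whose term is listed. A patient treated for early-stage disease who relapsed and then received only a TKI satisfies both definitions. The eligibility criteria do not exclude such patients, and recording stage at diagnosis separately from current stage anticipates that the two may differ.

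This row is one of seven in the SAP table ticked for OS, the primary efficacy outcome. Among the prior-treatment rows, only this one and prior chemotherapy carry OS. Those two rows handle adjuvant-only chemotherapy by different written rules. If footnote 2 is programmed literally, patients whose only treatment for metastatic disease was a TKI join the group meant to have had more. That would narrow any contrast between the groups and overstate the share with other prior therapy.

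**Working it through.** **Step 1: apply each rule to the patients in question.** Each is assumed to have received only a TKI for metastatic disease.

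| Earlier treatment | Footnote 1 | Footnote 2 and Appendix 6 | Footnote 3 (prior chemotherapy) |
|---|---|---|---|
| Adjuvant or neo-adjuvant chemotherapy only | TKI alone | TKI + Other | No |
| Listed lung resection for early-stage disease, no chemotherapy | TKI alone | TKI + Other | No |
| Neither | TKI alone | TKI alone | No |

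The first two rows show the conflict. It is confined to systemic therapy and surgery, because footnote 2 already limits radiotherapy to palliative use.

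**Step 2: look for a rule that settles it.** The SAP does not say that footnote 1 overrides footnote 2. SAP 4.2.3 gives only the footnote 2 description, so someone programming the receptor-status table from that section has no setting limit to apply. The SAP addendum replaces the TKI list but refers back to the SAP for Appendix 6. Both the SAP and the addendum enter 'not applicable' under changes from protocol.

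**Step 3: size.** The plan gives no figure for this split, so there is none to reproduce. The following is an illustration; none of its inputs is stated for these groups.

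- s = share of the FAS that is 'TKI alone' by footnote 1, assumed 0.3 to 0.5.
- r = share of those with an earlier listed resection or adjuvant therapy, assumed 0.1 to 0.3.
- Share of the FAS that moves = s × r: 0.3 × 0.1 = 0.03, up to 0.5 × 0.3 = 0.15.
- Share c of the reported 'TKI + Other' group that is 'TKI alone' by footnote 1 = s·r / (1 − s + s·r): 0.03/0.73 = 0.041, up to 0.15/0.65 = 0.231.

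Assume exponential OS with medians of 25 months ('TKI alone') and 21 months ('TKI + Other'), the two ends of the planning range in protocol 9.5. Assume also that the patients who move survive like the rest of 'TKI alone'. The reported 'TKI + Other' median t then solves

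(1 − c)·2^(−t/21) + c·2^(−t/25) = 0.5.

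| c | Median t (months) | Gap 25 − t (months) |
|---|---|---|
| 0 | 21.00 | 4.00 |
| 0.041 | 21.15 | 3.85 |
| 0.10 | 21.36 | 3.64 |
| 0.20 | 21.73 | 3.27 |
| 0.231 | 21.84 | 3.16 |
| 0.30 | 22.11 | 2.89 |

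Over the assumed shares the 'TKI + Other' median shifts by 0.15 to 0.84 months. For scale, the plan's own 95% CI at a 21-month median with all 3500 patients is 20.1 to 21.9, a half-width of (21.9 − 20.1)/2 = 0.9 months. A subgroup's interval would be wider.

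**The case against.** The best defence is that footnote 1 sets the boundary and footnote 2 only lists what counts as 'Other' within the metastatic setting. On that reading adjuvant-only and previously resected patients stay in 'TKI alone'. The reading is available, but the SAP does not state it and SAP 4.2.3 omits footnote 1. Footnote 2 can also be parsed as any treatment except TKIs, palliative radiotherapy and listed surgery. That would exempt advanced-disease surgery while leaving other surgery unexempted, which is less natural. It does show that the sentence needs rewording.

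Other points stand. Footnote 2 restricts radiotherapy to palliative use and surgery to a list labelled as advanced-disease surgery, so the authors did try to limit two of the three components. Separate subgroups may use different rules, so the difference from footnote 3 is not a contradiction in itself. The prior-chemotherapy row, which excludes adjuvant-only use, also carries OS, so the protocol's cohort commitment does not rest on this row alone. The analysis is descriptive and no tests are planned.

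A reader might go further and infer that the reported groups are misclassified, or that curative-intent operations are counted as advanced-disease treatment. The documents do not support this. They show neither the programmed rule nor the number of patients affected, and Appendix 6 states no intent for any procedure. That a listed lobectomy may have been done for early-stage disease is a possibility which the list fails to rule out.

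**Conclusion.** The concern holds as an inconsistency of definition. Footnotes 1 and 2 are not complements, and Appendix 6 cannot separate early-stage from advanced-disease resections. Applied as written, footnote 2 and Appendix 6 put some patients in the group that footnote 1, and the protocol's description of the cohorts, would keep them out of. Misclassification is possible; it is not shown.

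The number affected is unknown. The 3.85 to 3.16 month figures depend on assumed shares, exponential OS and medians borrowed from a whole-population planning range. They show only that a small affected share matters little and a large one visibly narrows the contrast. The issue is confined to results by prior therapy type: the OS, PFS, TTD and RR subgroup outputs with their demographics, and the receptor-status table. Overall FAS results are unaffected. The SAP should be corrected because the row carries the primary efficacy outcome and the remedy is cheap.

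**What to change.** 1. State in footnote 2 and in SAP 4.2.3 that footnote 1's metastatic-setting limit governs the split, and say how it applies to stage IIIB disease, which the protocol also admits.
2. Exclude adjuvant-only and neo-adjuvant-only systemic therapy from 'Other', as footnote 3 does for prior chemotherapy.
3. Count the lung-resection and lymphadenectomy terms in Appendix 6 as 'Other' only when stage at diagnosis was IIIB or IV, or by procedure date if the CRF holds it. Give a default for missing stage.
4. Report how many patients change group between the footnote 2 reading and the corrected rule.

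The cost is SAP wording and one derivation. Stage at diagnosis is collected, and footnote 3 presupposes that adjuvant use can be identified. Whether surgery dates exist must be confirmed, since the protocol lists prior surgery only as yes/no. Without dates, stage at diagnosis is an imperfect proxy: a patient diagnosed early who had a listed resection after relapse would be left out of 'Other'.
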